## 10.3 Adjustments for Covariates

Baseline value of the efficacy endpoints that will be analyzed will be included as covariate in the models.

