24. The PROs/assessments will all be completed prior to dosing and procedures during the study visit (see section 11.1).
25. The CAF and ESS will be administered prior to dosing and procedures during the study visit (see section 11.1.2 and 11.1.3).
26. The Modified Hoehn and Yahr will be administered at screening prior to other procedures (see section 11.1.1).
27. All concomitant medications will be recorded from screening through Day 210 (see section 9.3).
28. During Screening (post-consent), only SAEs related to a study-specific procedure will be collected. For all related AEs of moderate or severe intensity ongoing at the end of the study, follow-up will continue until the event has resolved to baseline severity, the event is assessed as stable by the Investigator, or the patient is lost to follow-up or the patient withdraws consent (see section 12).
29. Drug accountability must be performed at each visit with the exception of screening, baseline and day 210 (safety follow up) (see section 6.4).
30. Where drug is dispensed, the remainder of the previous bottle should be collected and retained by the site.
31. Study drug should be administered in clinic with food.

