9.2 Visit Specific Procedures

9.2.1 Visit 1 / Screening

The Screening visit must be performed within 42 days prior to Day 1 – Baseline. The following procedures will be performed at the Screening visit:

- Subjects or their Legally Authorized Representative (LAR) (or designee as applicable by local law) must provide written informed consent to the study procedures prior to any study procedures. The caregiver must also provide written informed consent at this time.
- Evaluate subject eligibility against study inclusion/exclusion criteria.
- Confirm DLB diagnosis (see section Appendix B).
- Record demographic information, confirm ethnicity, alcohol and drug history, educational history and obtain medical history.
- Administer the Mini-Mental State Exam (MMSE) and Geriatric Depression Scale (GDS)
- Administer Modified Hoehn and Yahr
- Administer CAF and ESS
- Administer C-SSRS Screening/Baseline version
- Perform complete physical examination with neurological examination
- Measure and record vital signs
- Perform 12-lead ECG
- MRI (or CT scan due to contraindication of MRI, if approved by medical monitor), unless an historical MRI/CT scan is used.
- Draw blood and prepare samples for APOE status. Apolipoprotein E (ApoE) genotype is associated with the risk and age of onset of DLB. Blood samples (approximately 10 mL) to perform this testing will be collected and will be utilized to further understanding of response to CT1812. The genotyping is mandatory for participation in the study and the results will not be revealed to either the investigator or subject and caregiver.
- Draw blood and prepare samples for coagulation testing (PT/INR), serum chemistry, hematology, viral serology, TSH, FSH (in women who had their last natural menses less than 24 months prior to screening and who are not surgically sterile) and HbA1c (in known

diabetics), Blood should be drawn within an hour of urine collection. Abnormal results at screening will exclude a subject unless the investigator is aware of a specific reason that can explain the abnormality (e.g., elevated CPK 24 hours after strenuous exercise). Should an abnormal lab remain abnormal on repeat the subject will be excluded. Collect blood sample for exploratory biomarker samples

- Collect blood samples for exploratory plasma biomarker analysis
- Collect urine sample for β -HCG pregnancy test for women who are not postmenopausal (last natural menses was less than 24 months ago) that are not surgically sterile.

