9.2.2 Visit 2 / Study Day 1 – Baseline

The following procedures will be conducted on Day 1:

Pre-dose Assessments:

- Confirm continued eligibility prior to dosing.
- Administer MOCA, CDR, ADCS-ADL, NPI, ADCS-CGIC, MDS-UPDRS Part III, CAF and ESS
- Administer C-SSRS Since Last Visit version
- Perform complete physical examination with neurological examination
- Measure and record vital signs
- Draw blood and prepare sample for serum chemistry and hematology Blood should be drawn within an hour of urine collection.
- Collect whole blood sample for future biomedical research including potential genetic analyses
- Collect blood samples for PK and exploratory plasma biomarker analysis
- Collect urine samples for urinalysis
- Record any new medical conditions, AEs, or changes in medications since the Screening visit.
- Administer study drug with food.

Post-dose Assessments

- Record ECG ~1- 2 hours post-dose
- Dispense study drug supply and instructions for at home dosing.
- Instruct subject to return for Day 14 visit including instructions to bring study drug to the Day 14 visit

9.2.3 Visit 3 Study Day 14

The subject will return to the clinic for the following assessments:

- Measure and record vital signs
- Draw blood and prepare sample for serum chemistry and hematology. Blood should be drawn within an hour of urine collection.
- Collect urine samples for urinalysis,
- Record any AEs.
- Record changes in medications.
- Conduct drug accountability, return study drug to the subject for continued dosing
- Instruct subject to return for Day 28 visit including instructions to hold dose on morning of Day 28 visit and to bring study drug with them

9.2.4 Visit 4 Study Day 28

The subject will return to the clinic for the following assessments:

Pre-dose Assessments:

- Administer MOCA, CDR, ADCS-ADL, NPI, ADCS-CGIC, MDS-UPDRS Part III, CAF and ESS
- Administer C-SSRS Since Last Visit version
- Perform brief physical examination
- Measure and record vital signs
- Draw blood and prepare sample for serum chemistry and hematology.) Blood should be drawn within an hour of urine collection
- Collect blood samples for PK and exploratory plasma biomarker analysis

- Collect urine samples for urinalysis
- Record any AEs.
- Record changes in medications.
- Conduct drug accountability
- Collect remaining drug in old bottle.
- Administer Day 28 dose with food.

Post-dose Assessments:

- Record ECG ~1- 2 hours post -dose).

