## 10.2 Baseline Values

Unless otherwise noted, baseline is defined as the last non missing value recorded before or on the date of first dose of study drug. Unscheduled visits will be used in the determination of baseline values, when applicable.

For all efficacy assessments, baseline will be considered as the latest assessment conducted within 6 hours after the first dose of study drug.

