### 11.2 Epworth Sleepiness Scale (ESS)

The ESS total score will be analyzed as described in Section 11.1. Plots of mean ESS total score change from baseline with standard deviation over time, plots of LS mean ESS total score (from MMRM model) change from baseline with 95% CI over time, and spaghetti plots of individual

subject ESS total score change from baseline over time will be provided for the ITT population only. A listing for individual ESS scores will be presented.

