### 11.3 Clinician Assessment of Fluctuation (CAF)

The CAF severity score will be analyzed as described in Section 11.1. Plots of mean CAF severity score change from baseline with standard deviation over time, plots of LS mean CAF severity score (from MMRM model) change from baseline with 95% CI over time, and spaghetti plots of individual subject CAF severity score change from baseline over time will be provided for the ITT population only. A listing for individual CAF scores will be presented.

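### CAF and ESS are each read twice before treatment but the MMRM adjusts for one reading; adding the other would cut residual variance by nil to about 20%, depending on correlations the documents do not give

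*SAP*

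**What the plan says.** **Two readings before treatment.** The Screening list in Protocol 9.2.1 includes "Administer CAF and ESS". The Day 1 pre-dose list in 9.2.2 includes both again: "Administer MOCA, CDR, ADCS-ADL, NPI, ADCS-CGIC, MDS-UPDRS Part III, CAF and ESS". The notes to Table 1 (Protocol 9.1) confirm the order on the day: "The CAF and ESS will be administered prior to dosing and procedures during the study visit". The two readings can be up to six weeks apart: "The Screening visit must be performed within 42 days prior to Day 1 – Baseline". In Table 1 the other efficacy scales start on Day 1, so CAF and ESS are the only efficacy endpoints with a repeat reading.

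**One reading in the model.** Under the general rule of SAP 10.2, "baseline is defined as the last non missing value recorded before or on the date of first dose of study drug". A separate sentence there, for efficacy, also takes a single value, the latest. SAP 10.3 then states: "Baseline value of the efficacy endpoints that will be analyzed will be included as covariate in the models". The MMRM in SAP 11.1 models change from baseline with one baseline covariate, and the two scales inherit it: "The ESS total score will be analyzed as described in Section 11.1" and "The CAF severity score will be analyzed as described in Section 11.1".

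The SAP gives the screening CAF and ESS no analytic role, except a possible fallback under the general rule. It gives no reason for leaving them out. SAP 10.4 and Protocol 15 rule out imputation of missing values.

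**The concern.** CAF is an informant rating of a symptom that varies by its nature, and ESS is a self-report covering two weeks. A single reading is an imperfect measure of a subject's usual level. A second reading, also untouched by study drug, may predict the outcome beyond the first. Neither scale has an eligibility cut-off in Protocol 8.2 or 8.3, so screening scores are not truncated by selection on their own value.

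What is at stake is precision on two endpoints specific to DLB, in a trial of about 40 subjects per arm. The validity of the planned comparison is not in question.

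**Working it through.** **The plan's own figure.** The only design calculation is for MoCA (Protocol 14.2, SAP 5): difference 0.78, SD 1.32, two-sided 0.05, 80% power, 105 subjects, combined CT1812 against placebo at 2:1.

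- Normal approximation: placebo n = (1.960 + 0.842)² × 1.32² × (1 + 1/2) / 0.78² = 33.7, so 34, and 102 in total.
- Exact t-test: 79.6% power at 34/68 and 80.7% at 35/70. So 105 reproduces.

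No such figure is given for CAF or ESS. The documents also give no within-subject correlations for either scale, so every correlation below is an assumption.

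**Formula.** Assume equal variances and consider the Day 182 comparison. Let r0 = corr(Screening, Day 1), r1 = corr(Day 1, Day 182) and r2 = corr(Screening, Day 182). With Day 1 alone the residual variance is proportional to 1 − r1². Adding Screening reduces it by the fraction

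(r2 − r1·r0)² / [(1 − r0²)(1 − r1²)].

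**Case A: all three correlations equal to ρ.** The fraction becomes ρ²/(1 + ρ)².

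| ρ | Day 1 only, 1 − ρ² | Both, 1 − 2ρ²/(1 + ρ) | Reduction |
|---|---|---|---|
| 0.3 | 0.910 | 0.862 | 5.3% |
| 0.5 | 0.750 | 0.667 | 11.1% |
| 0.6 | 0.640 | 0.550 | 14.1% |
| 0.7 | 0.510 | 0.424 | 17.0% |
| 0.8 | 0.360 | 0.289 | 19.8% |

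**Case B: Screening and Day 1 closer to each other than to Day 182.**

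| r0 / r1 / r2 | Reduction |
|---|---|
| 0.8 / 0.6 / 0.55 | 2.1% |
| 0.9 / 0.6 / 0.6 | 3.0% |
| 0.8 / 0.5 / 0.5 | 3.7% |
| 0.75 / 0.65 / 0.60 | 5.0% |
| 0.7 / 0.5 / 0.5 | 5.9% |
| 0.8 / 0.6 / 0.6 | 6.3% |

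The edges of this case are wider: 0.1% at 0.9/0.6/0.55 and 10.7% at 0.8/0.7/0.7.

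**Case C: AR(1)-type decay, r2 = r0·r1.** The numerator is zero, so there is no gain. This requires scores without measurement error. Suppose instead reliability 0.7 and true-level correlations of 0.95 (Screening to Day 1) and 0.80 (Day 1 to Day 182). The observed correlations are 0.7 × 0.95 = 0.665, 0.7 × 0.80 = 0.56 and 0.7 × 0.95 × 0.80 = 0.532. The reduction is (0.532 − 0.3724)² / (0.5578 × 0.6864) = 6.7%.

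**Cost of the extra covariate.** Simulated ANCOVA with 35 and 70 subjects gives these net reductions in the variance of the treatment estimate: about 4.5%, 12% and 18% at equal ρ of 0.3, 0.6 and 0.8; 2.6% at 0.8/0.5/0.5; and −0.5% at 0.8/0.6/0.48 (AR(1) decay).

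**What this buys.** For an endpoint that would have 80% power, a reduction of 3.7% gives 81.5%, 11.1% gives 84.4% and 19.8% gives 87.9%. For ESS, take the cross-sectional SD of 5 in Protocol 11.1.3 and 35/70 subjects. The detectable difference is 2.802 × residual SD × √(1/35 + 1/70). At equal ρ it falls from 2.77 to 2.69 (0.3), from 2.51 to 2.37 (0.5) and from 1.74 to 1.56 (0.8).

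**The case against.** One prespecified rule for every efficacy endpoint, with the latest baseline as covariate, is conventional and valid. That stands: the SAP contains no error here, only an unused option.

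A reader might infer that the plan discards 5–20% of residual variance outright, or that CAF and ESS need 16–25% more subjects as a result. The documents do not support either. The 5–20% range needs equal correlations over a gap of at most 42 days and one of about six months. The 16–25% figure is 1/(1 − reduction) for equal correlations of 0.6 to 0.8 only.

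Nor does noise in the scales by itself argue for a large gain. With equal correlations the proportional gain shrinks as ρ falls: 8.2% at 0.4 against 19.8% at 0.8. If the two visits are less than two weeks apart, the ESS recall periods overlap, which points towards Case B.

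The stakes are also limited. Safety is the primary objective, MoCA is the key efficacy endpoint (SAP 10.7), and CAF and ESS are tested without multiplicity control and have no power target.

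Three practical objections have to be met in the wording:

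- Substituting for a missing screening score is imputation, which SAP 10.4 excludes.
- Re-screening is allowed (Protocol 5.3.1), so a subject may have more than one screening score.
- The efficacy sentence in SAP 10.2 refers to a window of six hours after the first dose, while the Protocol requires assessment before dosing. Those passages need reconciling in their own right, and the added covariate rule must name the pre-dose score.

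These points affect the drafting. They do not remove the case for using data already collected.

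**Conclusion.** The point holds as a modest efficiency improvement. Two pre-treatment readings of CAF and ESS are scheduled and one is used. The likely gain runs from nil to about 20% of residual variance: 5–20% with equal correlations of 0.3–0.8, about 2–7% in the central cases where Screening and Day 1 are more alike, and nil under AR(1) decay without measurement error. All of these rest on assumed correlations and on a single-visit approximation to the MMRM. The downside is very small, about half a percent in the simulated worst case.

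It should not be read as a finding of bias. Adjusting for either one or two pre-treatment scores leaves the randomised comparison valid. Nor does it touch MoCA, which has no screening value, or the sample size.

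**What to change.** Add to SAP 10.3, and refer to it from 11.2 and 11.3, before unblinding:

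*For CAF and ESS, the MMRM includes both the Day 1 pre-dose score and the last screening score before Day 1 as covariates; change from baseline remains defined from Day 1. If the screening score is missing, the Day 1 score is entered for that covariate only, as an exception to Section 10.4; no outcome values are imputed.*

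Naming the last screening score settles re-screened subjects. The fallback keeps subjects in the model and uses pre-treatment data only.

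The screening score should go in as a second covariate. Replacing the Day 1 covariate with the mean of the two scores, while change is still taken from Day 1, makes matters worse. With equal correlations the residual variance becomes 2(1 − ρ) − (1 − ρ)²/[2(1 + ρ)]. That is 0.917 against 0.750 at ρ = 0.5 (22% higher) and 0.389 against 0.360 at ρ = 0.8 (8% higher).

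The cost is one degree of freedom per model and one declared exception to the no-imputation rule, with no new data. If the blind has already been broken, SAP 6 makes the change post hoc, and it should be labelled so.

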10.4 Handling of Dropouts or Missing Data

Data in summary tables will be summarized by the nominal visit collected in the electronic data capture (EDC) system. The Day 182 (End of Study or early termination) label in the EDC system is used for both Day 182 End of Study and early termination visits. A participant will only have their Day 182 data included in the summary tables if it occurs on or after study Day 170. Participants who early terminate before study day 170 will have their early termination visit data listed only. No imputations will be made for missing values. Summaries will be based on observed data only.

10.5 Interim Analysis and Data Monitoring

No interim analysis is planned for this study.

A DSMB will oversee the safety of the trial. This committee will include independent experts, including an independent statistician. Safety data will be provided to the DSMB at quarterly intervals during the trial. The study clinician and study medical monitor will review trial safety data biweekly and more frequently as the safety data warrant. Similarly, more frequent ad hoc meetings of the DSMB will occur if ongoing safety data indicate interim meetings are indicated.

10.6 Examination of Subgroups

The following subgroups are defined for this study:

Subgroup	Definition/Levels
Sex	Male, Female
MMSE at Baseline	18-24, 25-27
Age	<Median age, >=Median age
Amyloid positivity at Screening	The C2N Amyloid Probability Score 2 (APS2) in plasma will be used. The APS2 score will be calculated (by C2N) at screening/baseline in plasma. If the APS2 is >47.5, the participant will be included in the amyloid-biomarker positive subgroup. Otherwise, the participant will be included in the amyloid-biomarker negative subgroup. If a participant does not have the APS2 score available, then classification will be based on the plasma pTau217/Tau217 ratio only. If the pTau217/Tau217 ratio is >4.2, the participant will be included in the amyloid-biomarker positive subgroup. Otherwise, the participant will be included in the amyloid-biomarker negative subgroup.

COGNITION Therapeutics  
Protocol number: COG1201

Statistical Analysis Plan  
15 Nov 2024

	Note: The APS2 score is an output that takes into account plasma pTau217/Tau217 and the plasma Aβ42/40 ratio to predict the presence of brain amyloid >25 centiloids via PET.
Parkinsonian features at Baseline based on MDS-UPDRS	<Median baseline MDS-UPDRS3 total score, ≥Median baseline MDS-UPDRS3 total score
Parkinsonian features at Baseline based on Modified Hoehn and Yahr Scale	Baseline Modified Hoehn and Yahr stage ≤2 Baseline Modified Hoehn and Yahr stage >2
Acetylcholinesterase (AChE) inhibitors and/or memantine use during the study	Yes: Participant took these medications during the treatment period No: Participant did not take these medications during the treatment period The following medications will be considered for this subgroup: Any medication containing donepezil (Aricept, Namzaric), rivastigmine (Exalon), galantamine (Razadyne, Reminyl), or tacrine (Cognex) is considered an AChE inhibitor. Any medication containing memantine (Namenda, Namzaric) is considered memantine.
ApoE status at Baseline	Positive, Negative. If genotype ApoE or phenotype ApoE contains E4, then ApoE status is considered Positive. Otherwise Negative.
Skin biopsy sum total composite score at Baseline	Positive: Baseline skin biopsy sum total composite score >0 Negative: Baseline skin biopsy sum total composite score =0
Plasma pTau217/Tau217 ratio at Baseline	This subgroup will consist of three levels: 
 
Amyloid-biomarker positive, Baseline pTau217/Tau217 ratio < median
 
Amyloid-biomarker positive, Baseline pTau217/Tau217 ratio ≥ median
 

	

• Amyloid-biomarker negative

 
In the subset of subjects included in the amyloid-biomarker positive subgroup, the median Baseline pTau217/Tau217 ratio value will be determined using the data received from C2N. The subjects in the amyloid-biomarker positive subgroup will then be split into two groups based on their Baseline pTau217/Tau217 ratio value (< median, >= median).
 
All subjects in the amyloid-biomarker negative subgroup will be included in the “Amyloid-biomarker negative” group, regardless of their Baseline pTau217/Tau217 ratio value.

--	---

10.7 Multiple Comparison/Multiplicity

Although the assessment of efficacy is considered a secondary objective of this study, the key efficacy endpoint is defined as the change from baseline in MoCA score at 6 months. The primary analysis of this key efficacy endpoint will be based on the comparison of both CT1812 treatment groups combined vs. placebo. If the result of this analysis is statistically significant ( $p < 0.05$ ), then formal statistical testing will proceed as follows in a sequential manner:

1. CT1812 300mg/day vs. placebo
2. CT1812 100mg/day vs. placebo

If the comparison of CT1812 300mg/day vs. placebo is statistically significant ( $p < 0.05$ ) then the comparison of CT1812 100mg/day vs. placebo will be formally tested. If the comparison of CT1812 300mg/day vs. placebo is not statistically significant ( $p \geq 0.05$ ) then the result of the analysis of CT1812 100mg/day vs. placebo will be interpreted descriptively.

No adjustments for multiplicity will be made for the testing of the other endpoints evaluated in this study.

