A Phase 1a/2 trial (COG0102), evaluated the safety and pharmacokinetics of three doses of once-a-day CT1812 (90 mg, 280 mg, 560 mg) dosed for 28 days in subjects with mild to moderate Alzheimer's disease. This study enrolled 19 subjects in a 1:1:1:1 ratio of these doses vs. placebo. In general, all doses were relatively well tolerated, with no SAEs. All AEs were considered mild or moderate. While there was an increased frequency observed in total AEs with increasing dose, the small number of treated subjects does not permit definitive conclusions regarding the incidence of AEs by dose in a larger study population. Specific AEs which were noted to occur with greater frequency at the 560 mg dose included transient lymphocytopenia, nausea, vomiting, headache, fatigue, and depression. These AEs resolved in most instances while treatment was ongoing; one subject at the 560 mg dose experienced an ALT increase of 4.7 X ULN which resolved to normal levels after discontinuation of study drug. Cognitive outcomes were similar across the treatment groups. Plasma CT1812 concentration increased approximately dose proportionally, with a dose dependent increase in CSF concentration. CSF concentrations at all tested doses were > 80% of estimated brain PGRMC-1 receptor occupancy, which was the threshold associated with efficacy in preclinical studies.

A Phase 1 trial (COG0105) was a pilot study of Synaptic Vesicle Glycoprotein 2A (SV2A) PET ligand ¹¹C-UCB-J to evaluate the effect of CT1812 treatment on synaptic density in subjects with Mild to Moderate Alzheimer's Disease. Eligible subjects were randomized in a 1:1:1 (300 mg CT1812: 100 mg CT1812: placebo) ratio. This was a 24-week treatment period, with an optional 24-week double blind extension period which was instituted after study startup; 23 subjects were dosed, 18 completed the original trial, and 13 rolled over to the double-blind extension.

Overall, CT1812 was generally well tolerated when delivered daily over a 24- or 48-week period in subjects with mild to moderate AD.

The most common TEAE in the CT1812 treatment arms was headache. Two subjects were withdrawn from the study due to TEAEs of liver function test increased (mild, probably related to

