3.5 Rationale for Selected Doses

Based on brain receptor occupancy studies in animals, the daily dose of 300 mg/day is projected to exceed 95% occupancy while the 100 mg/day dose is projected to exceed 80% receptor occupancy. In the Phase 1 multiple dose 2-week trial, doses exceeding 300 mg/day were well-tolerated in both younger (≤ 64 years of age) and older (≥ 65 years of age) subjects. Transient increases in LFTs were noted in some subjects. Subjects were discontinued and LFTs returned to normal after discontinuation. In the phase 1 AD trial tolerability was also acceptable with no severe or serious adverse events observed at doses exceeding 300 mg/day.

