## 6. GENERAL ANALYSIS CONSIDERATIONS

The statistical analyses will be reported using summary tables and listings. The International Council for Harmonisation of Technical Requirements for Pharmaceuticals for Human Use (ICH) numbering convention will be used for all tables, listings, and figures (TLFs). Unless otherwise noted, all statistical testing will be 2-sided and performed at the 0.05 significance level. Tests for the key efficacy endpoint of change from baseline in MoCA score at Month 6 will be declared statistically significant if the calculated  $P$  values following the sequential testing hierarchy described in Section 10.7 are  $<0.05$ . No adjustments for multiple comparisons will be made for the statistical testing of any other endpoints.

Continuous variables will be summarized by presenting the number of observations, means, standard deviations (SDs), medians, minimums, and maximums. Other summaries (e.g., quartiles, 95% confidence intervals [CIs]) may be used as appropriate.

Categorical variables will be summarized by presenting counts and percentages of subjects in corresponding categories. All possible categories as defined in the eCRF should be populated, even if they have zero counts. Percentages for missing values are omitted and do not account for the percent calculation of other categories. Percentages are based on the total category count excluding the missing category if not otherwise mentioned. In certain tables (e.g., AEs), the total number of subjects is used as the denominator. Footnotes will specify the percent basis in those cases.

All summary tables will be presented by treatment group. Baseline summaries will also include a total summary column.

Individual subject data obtained from the eCRFs, external vendors, central and local clinical laboratory and any derived data will be presented by subject in data listings.

The analyses described in this plan are considered a priori, in that they have been defined before breaking the blind.

Any analyses performed after breaking the blind will be considered post hoc and exploratory. Post hoc analyses will be labeled as such on the output and identified in the CSR.

All analyses and tabulations will be performed using SAS® statistical software, version 9.4 or higher (SAS Institute Inc). Tables, listings, and figures will be presented in RTF and PDF format.

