## 11. METHODS OF EFFICACY ANALYSIS

### 11.1 Montreal Cognitive Assessment Scale (MoCA)

The primary efficacy comparison will test the following hypotheses:

- $H_0$ : The change from baseline in MoCA score at Month 6 is equal when comparing both active treatment groups (combined) versus Placebo.
- $H_1$ : The change from baseline in MoCA score at Month 6 is different when comparing both active treatment groups (combined) versus Placebo.

Baseline and both observed values and change from baseline values for Day 28, Month 3, and Month 6 will be summarized by treatment group using descriptive statistics.

The difference between treatment groups (combined CT1812 vs. placebo) will be assessed using a mixed model for repeated measures (MMRM) with change from baseline values at Day 28, Month 3, and Month 6 as the response values, treatment group (CT1812 100 mg, CT1812 300 mg, placebo), time point, and a treatment group by time point interaction as fixed effects, subject as a random effect, and baseline value as a covariate. An unstructured covariance structure will be applied, and the denominator degrees of freedom will be computed using the Kenward-Roger method. If the model does not converge using the unstructured covariance structure, the autoregressive (order 1) AR(1) structure will be used. If the AR(1) structure also does not converge, other covariance structures deemed appropriate to fit the data will be used. The least square means (LSM), standard errors, LSM differences between combined CT1812 and placebo, 95% CIs for the LSM differences, and p-values at each post-Baseline time point will be presented.

The pairwise comparisons of each CT1812 group and placebo will be performed from the same model in a similar manner to what is described above.

Plots of mean MoCA score change from baseline with standard deviation over time, plots of LS mean MoCA score (from MMRM model) change from baseline with 95% CI over time, and spaghetti plots of individual subject MoCA score change from baseline over time will be provided. These three plots will be repeated using the completers/compliers population.

Subgroup analysis will be done for MoCA scores using subgroups defined in Section 10.6.

A listing for individual MoCA scores will be presented.

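### SAP 10.7: the requirement that 300 mg be significant before 100 mg is formally tested is not needed to hold family-wise error at 5%, and it costs about 12 points of power for the 100 mg claim if both doses have the planned effect

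*SAP*

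**What the plan says.** SAP section 6 sets the general rule that "all statistical testing will be 2-sided and performed at the 0.05 significance level". It ties claims of significance on the key efficacy endpoint, change from baseline in MoCA at Month 6, to the hierarchy in SAP 10.7. For everything else, "No adjustments for multiple comparisons will be made for the statistical testing of any other endpoints".

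SAP 10.7 opens the hierarchy with the pooled contrast: "The primary analysis of this key efficacy endpoint will be based on the comparison of both CT1812 treatment groups combined vs. placebo". If that is significant, "then formal statistical testing will proceed as follows in a sequential manner": first 300 mg against placebo, then 100 mg against placebo. The 100 mg comparison is formal only if 300 mg has p < 0.05. If it does not, "then the result of the analysis of CT1812 100mg/day vs. placebo will be interpreted descriptively".

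All three contrasts come from one three-group MMRM. SAP 11.1 says: "The pairwise comparisons of each CT1812 group and placebo will be performed from the same model". Protocol 14.4.3 lists the combined and pairwise comparisons with no order among them. Neither document gives a reason for placing 300 mg ahead of 100 mg.

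**The concern.** A gate in a testing hierarchy normally pays for itself by protecting the family-wise error rate. Here the combined test has already provided that protection, so the second gate restricts the 100 mg claim without lowering the maximum error rate.

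The outcome at stake is a positive combined result with 100 mg significant and 300 mg missing. Under the plan that trial could make no formal claim for either dose, although a rule with the same 5% bound would allow one for 100 mg.

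The documents treat both doses as plausibly active. The primary efficacy contrast pools them, and Protocol 3.5 says "the 100 mg/day dose is projected to exceed 80% receptor occupancy". Protocol 3.3 describes that 80% level as one "which was the threshold associated with efficacy in preclinical studies".

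**Working it through.** **Inputs.** SAP 5: difference 0.78 points, SD 1.32, total N 105, power 80%, α 0.05. SAP 6: two-sided testing. Protocol synopsis: 1:1:1 allocation, hence 35 evaluable subjects per arm and 35 placebo against 70 active. Planned N is 120 (40 per arm), so 105/120 = 87.5% are assumed evaluable.

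**Reproducing the plan's figure.** The standard error is 1.32 × √(1/35 + 1/70) = 0.273, and the noncentrality is 0.78/0.273 = 2.86. The noncentral t gives 80.7% power (normal approximation 81.4%). A total of 105 is the smallest 1:1:1 sample that reaches 80%; 102 gives 79.6%. The stated 80% reproduces.

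**Logic.** Let δ300 and δ100 be the dose effects against placebo, with the combined effect (δ300 + δ100)/2. The three nulls are H300: δ300 = 0, H100: δ100 = 0, and Hcomb: δ300 + δ100 = 0. Any two of them imply the third, so every intersection is the same global null, and the combined test is a valid 0.05 test of it. Suppose both doses are tested in parallel at 0.05 after a significant combined test:

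- All three nulls true: any rejection needs the combined test to reject, with probability at most 0.05.
- Only H300 or only H100 true: the single true null is tested at 0.05.
- Only Hcomb true (equal and opposite effects): it is tested at 0.05.

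Family-wise error is therefore at most 0.05 in every configuration. This needs only that each contrast be a valid 0.05 test; it does not depend on the details of the MMRM.

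**Simulation.** 1,000,000 three-arm trials per scenario, 35 per arm, SD 1.32, pooled-variance t contrasts on 102 degrees of freedom. Monte Carlo standard error is about √(0.05 × 0.95/1,000,000) = 0.0002 for the error rates.

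Family-wise error:

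| True effects (300 mg / 100 mg) | Gated (SAP) | Parallel |
|---|---|---|
| 0 / 0 | 0.0499 | 0.0499 |
| 0 / 5 | 0.0498 | 0.0498 |
| 5 / 0 | 0.0502 | 0.0502 |
| 0.78 / −0.78 | 0.0504 | 0.0504 |
| 0.39 / 0 | 0.0177 | 0.0263 |

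Power for a formal 100 mg claim (only the first row uses the plan's effect for both doses; the other pairs are assumptions):

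| True effects (300 mg / 100 mg) | Gated | Parallel | Difference, points |
|---|---|---|---|
| 0.78 / 0.78 | 0.543 | 0.666 | 12 |
| 0.90 / 0.66 | 0.496 | 0.538 | 4 |
| 0.78 / 0.39 | 0.209 | 0.228 | 2 |
| 1.06 / 0.50 | 0.343 | 0.348 | 0.5 |
| 1.17 / 0.39 | 0.231 | 0.232 | 0.1 |
| 0.39 / 0.78 | 0.209 | 0.533 | 32 |
| 0.50 / 1.06 | 0.343 | 0.798 | 46 |

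With 0.78 in both doses, power for at least one formal dose claim is 0.666 gated and 0.789 parallel. With 40 per arm, the 100 mg figures are 0.615 and 0.728. Power for the combined and 300 mg tests is the same under both rules.

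**What depends on the combined gate.** Without it, testing both doses at 0.05 gives a family-wise error of 0.090 under the global null.

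**The case against.** The strongest reply is that the plan is a complete, pre-specified fixed sequence with strong error control, and that testing the higher dose first is conventional. That stands: there is no error, contradiction or bias here.

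Protocol 3.5 also projects more than 95% occupancy at 300 mg, in the same sentence that projects more than 80% at 100 mg. The documents therefore do give a plausible pharmacological basis for expecting 300 mg to do at least as well, although they do not offer it as the reason for the order. In that direction the loss is small, from 0.1 to 4 points in the cases above.

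The gate also does something short of the maximum error. Under the global null it lowers the chance of a false formal 100 mg claim from 0.027 to 0.010. With 300 mg at 0.39 and 100 mg at zero, it lowers it from 0.026 to 0.018. It also avoids a formal low-dose claim beside a missed high dose, a pattern that is awkward to interpret. A sponsor may value that.

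The stakes are limited. Safety is the primary objective, the documents state power only for the combined contrast, and SAP 11.1 reports the 100 mg estimate, interval and p-value whether or not the gate opens.

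A reader might infer that the gate routinely costs 30 to 45 points, or that liver-related stops would weaken the 300 mg arm. The documents support neither. The large losses need 300 mg to do worse than 100 mg, which is an assumption, and no dose-specific stopping rate is given that separates 300 mg from 100 mg.

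**Conclusion.** The point holds as an efficiency gain. The gate is not needed to keep family-wise error at 5%, and removing it lowers power for none of the three tests. At the planned effect in both doses, the gate costs about 12 points for the 100 mg claim and about 12 for any formal dose claim. The cost is about 4 points or less when 300 mg is the stronger dose, and larger only if 300 mg underperforms.

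Two stronger readings should be resisted. The SAP does not leave the family uncontrolled. Nor is it right that the gate gives no protection at all: it lowers some non-maximal error rates, but not the maximum.

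The error bound rests on keeping the combined test first and on there being exactly two doses. The power figures rest on SD 1.32, 35 evaluable subjects per arm and a single-time-point t contrast in place of the MMRM.

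**What to change.** In SAP 10.7, replace the two sequential steps and the paragraph that follows them with: *If the combined comparison is significant (two-sided p < 0.05), CT1812 300 mg vs placebo and CT1812 100 mg vs placebo will each be formally tested at two-sided 0.05 (closed testing procedure); otherwise both are descriptive.* Align the reference to the hierarchy in SAP section 6. Keep the combined comparison as the first gate.

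The cost is a few lines of wording, with no new analyses and no alpha spent. It must be done before unblinding, because SAP section 6 treats analyses performed after the blind is broken as post hoc. The documents do not show whether that window is still open. If the sponsor prefers 300 mg first for dose-response reasons, the SAP should state that reason and accept the power loss knowingly.
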